#### 5.5.1.2.3

#### **Criteria for permanent discontinuation of ipilimumab for Related Adverse Events**

Ipilimumab administration must be permanently discontinued if any of the following Related Adverse Events occurs:

- Any  $\geq$  Grade 2 eye pain or reduction of visual acuity that does not respond to topical therapy and does not improve to  $\leq$  Grade 1 severity within 2 weeks of starting therapy, OR, requires systemic treatment.
- Any  $\geq$  Grade 2 hypophysitis.
- Any  $\geq$  Grade 3 bronchospasm or other hypersensitivity reaction.
- Any other  $\geq$  Grade 3 non-skin related adverse event with the exception of events listed under “Exceptions to Permanent Discontinuation” (Section [5.5.1.2.4](#)).
- Any  $\geq$  Grade 4 laboratory abnormalities, except for specified exceptions (Section [5.5.1.2.4](#)).
- For AST, ALT, or Total Bilirubin, then as follows:
  - AST or ALT  $> 5 \times$  ULN.
  - Total Bilirubin  $> 3 \times$  ULN.
- Any other  $\geq$  Grade 4 adverse event except for specified exceptions (Section [5.5.1.2.4](#)).
- Stevens-Johnson syndrome, toxic epidermal necrolysis, or rash

complicated by full thickness dermal ulceration or necrotic, bullous, or hemorrhagic manifestations.

- Any adverse event, laboratory abnormality or intercurrent illness which, in the judgment of the investigator, presents a substantial clinical risk to the patient with continued dosing.
- Any motor or sensory neurologic toxicity  $\geq$  Grade 3 regardless of attribution.
- Diagnosis with Guillain-Barré syndrome or myasthenia gravis (any grade).
- Patients who require high dose steroids, other immune suppressants or anti-TNF drug therapy for the management of immune related adverse events as described in the Toxicity Management Guidelines/Algorithms should have ipilimumab permanently discontinued. Treatment with oral budesonide or moderate dose steroids for grade 2 colitis or grade 2 or lower skin rash or higher dose IV steroids for grade 3 skin rash are criteria for ipilimumab dose delay but not permanent discontinuation.

Rev. 9/14

#### 5.5.1.2.4

#### **Exceptions to permanent discontinuation of ipilimumab on Arms C and F (ipilimumab 3mg/kg)**

Ipilimumab administration may be resumed in the following cases:

- Potentially reversible inflammation (< Grade 4), attributable to a local anti-tumor reaction and a potential therapeutic response. This includes inflammatory reactions at sites of tumor resections or in draining lymph nodes, or at sites suspicious for, but not diagnostic of metastasis.
- Laboratory abnormalities that are rapidly reversible, not life threatening, do not reflect underlying organ system dysfunction, and are not related to the study treatment, such as transient elevations of uric acid, hypocalcaemia, hypophosphatemia.
- Hospitalization for  $\leq$  Grade 2 adverse events (not including Grade 2 events

that require permanent discontinuation as listed under Section [5.5.1.2.3](#)) where the primary reason for hospitalization is to expedite the clinical work-up.

- Patients with the following conditions where in the investigator's opinion continuing study drug administration is justified:
  - Ocular toxicity that has responded to topical therapy and has improved to ≤ Grade 1 severity within 2 weeks of starting therapy.
  - Patients without a diagnosis of hypophysitis who have Grade 2 hypothyroidism, Grade 2 low testosterone or Grade 2 adrenal insufficiency where clinical symptoms are controlled with appropriate hormone replacement therapy.

**NOTE:** A patient on E1609 ipilimumab treatment arms (**Arm A and Arm C or Arm D and Arm F, respectively**) who experiences disease recurrence but was still considered surgically operable and can be rendered disease free by surgery should be reported as disease recurrence. However, in the absence of limiting toxicities per protocol criteria, such a patient may be offered additional ipilimumab therapy on protocol that must be captured on the usual forms (including treatment forms, toxicity forms, long term follow up for subsequent recurrence). In such a case the patient would re-start ipilimumab treatment at the next scheduled dose when medically cleared by his treating physician investigator.

### 5.5.1.3 **Immune-Related Adverse Events (irAEs): Definition, Monitoring, and Treatment**

Blocking CTLA-4 function may permit the emergence of auto-reactive T cells and resultant clinical autoimmunity. Rash/vitiligo, diarrhea/colitis, uveitis/episcleritis, hepatitis,

Rev. 8/12

Rev. 9/14

and hypopituitarism were drug-related, presumptive autoimmune events, now termed irAEs, noted in previous ipilimumab studies.

For the purposes of this study, an irAE is defined as an AE of unknown etiology associated with drug exposure and consistent with an immune phenomenon. Efforts should be made to rule out neoplastic, infectious, metabolic, toxin or other etiologic causes prior to labeling an AE an irAE. Serological, immunological, and histological (biopsy) data should be used to support the diagnosis of an immune-mediated toxicity. Suspected irAEs must be documented on an AE or SAE form.

Patients should be informed of and carefully monitored for evidence of clinically significant systemic irAE (e.g., systemic lupus erythematosus-like diseases) or organ-specific irAE (e.g., rash, colitis, uveitis, hepatitis or thyroid disease). If an irAE is noted, appropriate work-up (including biopsy if possible) should be performed, and steroid therapy may be considered if clinically necessary. See [Appendix XIII](#) for suggested work-up and treatment of irAEs.

It is unknown if systemic corticosteroid therapy has an attenuating effect on ipilimumab activity. However, clinical anti-tumor responses have been maintained in patients treated with corticosteroids and discontinued from ipilimumab. If utilized, corticosteroid therapy should be individualized for each patient.

Corticosteroid replacement therapy is not allowed except for patients who develop endocrinopathies during this study that require corticosteroid replacement therapy (such as hydrocortisone) at stable doses.

Prior experience suggests that diarrhea and/or colitis that is persistent or severe requires corticosteroid treatment. See [Appendix XIV](#) for GI Management Algorithm for additional details.

Rev. 11/13

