Given that serious adverse events may occur with ipilimumab and IFN $\alpha$  and that these may impact a patient's wellbeing, it is possible that the occurrence of other SAEs may seriously impact an underlying state of mental depression and lead to suicidal ideation. Therefore, patients should be carefully screened for depression at baseline and if there are indications or a history of depression it is strongly recommended that these patients be closely followed together with behavioral health or psychiatric medical support. Patients with an established diagnosis of depression that, in the assessment of the investigator may make the administration of IFN $\alpha$  or ipilimumab hazardous, should not be enrolled on this protocol. The risks and benefits of being treated with standard adjuvant IFN $\alpha$  should be weighed very carefully in consultation with behavioral health or psychiatry.

3.1.12 Patients must not have a documented history of inflammatory bowel disease (including ulcerative colitis and Crohn's disease) or diverticulitis (history of diverticulosis is allowed).

Documented history of inflammatory bowel disease?

Yes \_\_\_\_\_ No \_\_\_\_\_

History of diverticulitis?

Yes \_\_\_\_\_ No \_\_\_\_\_

3.1.13 Patients must not have autoimmune disorders or conditions of immunosuppression that require current ongoing treatment with systemic corticosteroids (or other systemic immunosuppressants), including oral steroids (i.e., prednisone, dexamethasone) or continuous use of topical steroid creams or ointments or ophthalmologic steroids. A history of occasional (but not continuous) use of steroid inhalers is allowed. Replacement doses of steroids for patients with adrenal insufficiency are allowed. Patients who discontinue use of these classes of medication for at least 2 weeks prior to randomization are eligible if, in the judgment of the treating physician investigator, the patient is not likely to require resumption of treatment with these classes of drugs during the study.

Exclusion from this study also includes patients with a history of symptomatic autoimmune disease (e.g., rheumatoid arthritis, systemic progressive sclerosis [scleroderma], systemic lupus erythematosus, Sjögren's syndrome, autoimmune vasculitis [e.g., Wegener's Granulomatosis]); motor neuropathy considered of autoimmune origin (e.g., Guillain-Barre Syndrome and Myasthenia Gravis); other CNS autoimmune disease (e.g., poliomyelitis, Multiple sclerosis).

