Patients with autoimmune hypothyroid disease or type I diabetes on replacement treatment are eligible.

Treatment with systemic corticosteroids (including oral steroids)?

Yes \_\_\_\_\_ No \_\_\_\_\_

Continuous use of topical steroid creams/ointments?

Yes \_\_\_\_\_ No \_\_\_\_\_

Continuous use of steroid containing inhalers?

Yes \_\_\_\_\_ No \_\_\_\_\_

Adrenal insufficiency?

Yes \_\_\_\_\_ No \_\_\_\_\_

Date of last dose of steroid containing medicines \_\_\_\_\_

3.1.14 Due to the possible effect of treatment with ipilimumab on the immunologic response to infectious disease vaccines, patients must not have had any infectious disease vaccination (e.g., standard influenza, H1N1 influenza, pneumococcal, meningococcal, tetanus toxoid) within 4 weeks prior to randomization.

Has the patient had an infectious disease vaccine within the past four weeks?

Yes \_\_\_\_\_ No \_\_\_\_\_ Date of vaccine \_\_\_\_\_

3.1.15 Patients must not be prisoners or subjects who are compulsorily detained (involuntarily incarcerated) for treatment of either a psychiatric or physical (e.g., infectious) illness. This is due to concerns about subject safety and compliance with study procedures.

Is the patient a prisoner or involuntarily incarcerated?

Yes \_\_\_\_\_ No \_\_\_\_\_

3.1.16 Patients who have other current malignancies are not eligible. Patients with other malignancies are eligible if they have been continuously disease free for > 5 years prior to the time of randomization. Patients with prior history at any time of any in situ cancer, lobular carcinoma of the breast in situ, cervical cancer in situ, atypical melanocytic hyperplasia or melanoma in situ are eligible. Patients with prior history of basal or squamous skin cancer are eligible. Patients who have had multiple primary melanomas are eligible.

Other current malignancies? Yes \_\_\_ No \_\_\_\_\_

Type of malignancy \_\_\_\_\_

Other previous malignancies? Yes \_\_\_ No \_\_\_\_\_

Type of malignancy \_\_\_\_\_

Disease-free? Yes \_\_\_\_\_ No \_\_\_\_\_

Date of last treatment \_\_\_\_\_

3.1.17 Women must not be pregnant or breast-feeding due to the unknown effects of ipilimumab and HDI on conception and the fetus. All females of childbearing potential must have a blood test or urine study during screening to rule out pregnancy. Please see Section [7.1.5](#) for required pregnancy testing prior to and during treatment.

Female? \_\_\_\_\_ (Yes or No)

Date of blood test or urine study: \_\_\_\_\_

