5.2.2.5 Self Administration of Subcutaneous Doses

Patients who are deemed competent to self administer the subcutaneous maintenance doses of IFN Alfa - 2b may do so following the first 4 weeks of treatment. Interferon Alfa-2b should be prescribed in 10 million unit vials with instructions to reconstitute with 1 ml of diluent to reach a final concentration of 10:1. See [Appendix X](#) for directions and patient IFN information guide. Patients must complete the E1609 Patient Diary -Interferon ([Appendix IV](#)).

5.2.2.6 Corticosteroids and other immunosuppressive medications are contraindicated during IFN Alfa-2b therapy because of immune suppressive effects. No systemic treatment with steroids (including creams) is permitted. Exception: patients may receive antihistamines and inhaled steroids may be permitted at dosages that are not systematically

Rev. 2/14

immunosuppressive if there is no alternative medication. Also, steroids (topical, inhaled or systemic) may be used to treat adverse events or toxicities if there is a clear clinical indication.

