- Grade  $\geq$  2 laboratory abnormalities that are secondary to an immune-related adverse event or autoimmune phenomenon (e.g., Grade  $\geq$  2 TSH associated with a CTCAE v.4 grade 2 thyroid dysfunction induced by ipilimumab, anemia, neutropenia, amylase, lipase, CPK, hyperglycemia, or elevated LFTs) should also lead to an ipilimumab dosing delay/skipping.
- Any other  $\geq$  Grade 3 laboratory abnormality.
- Any  $\geq$  Grade 3 skin-related adverse event (including IRAEs) **regardless of attribution**.

5.5.1.1.2 **Criteria to resume ipilimumab treatment on Arms A or D (ipilimumab 10mg/kg)**

Ipilimumab **may not** be restarted while the patient is being treated with oral or intravenous corticosteroids for the management of immune related adverse events except for patients on stable doses of hormone replacement therapy for adrenal insufficiency such as hydrocortisone. In addition, patients must be off and have no requirement for oral/I.V. corticosteroids for at least 1 week and meet the other criteria for retreatment as outlined below.

Restart ipilimumab dosing if/when the adverse event(s) resolve(s) to  $\leq$  Grade 1

Rev. 2/14

severity or returns to baseline within 3 weeks of last dose administration:

- If the adverse event has resolved (to  $\leq$  Grade 1 severity or returns to baseline), restart ipilimumab dosing at the next scheduled time point per protocol.
- If the adverse event has not resolved in the protocol-specified dosing window (3 weeks [+/- 3 days], the next scheduled dose will be omitted.
- Patients with Grade 1 diarrhea and/or colitis who require steroid therapy must have resolution to grade 0 (baseline) before resuming dosing with ipilimumab. Patients with Grade  $\geq 2$  related diarrhea and/or colitis must have ipilimumab permanently discontinued (Section [5.5.1.1.3](#)).

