#### 5.5.1.1.4

#### **Exceptions to permanent discontinuation of ipilimumab on Arms A and D (ipilimumab 10mg/kg)**

Ipilimumab administration may be resumed in the following cases:

- Potentially reversible inflammation ( $<$  Grade 4), attributable to a local anti-tumor reaction and a potential therapeutic response. This includes inflammatory reactions at sites of tumor resections or in draining lymph nodes, or at sites suspicious for, but not diagnostic of metastasis.
- Laboratory abnormalities that are rapidly reversible, not life threatening, do not reflect underlying organ system dysfunction, and are not related to the study treatment, such as transient elevations of uric acid, hypocalcaemia, hypophosphatemia.

- Hospitalization for  $\leq$  Grade 2 adverse events (not including Grade 2 events that require permanent discontinuation as listed under Section [5.5.1.1.3](#)) where the primary reason for hospitalization is to expedite the clinical work-up.
- Patients with the following conditions where in the investigator's opinion continuing study drug administration is justified:
  - Ocular toxicity that has responded to topical therapy and has improved to  $\leq$  Grade 1 severity within 2 weeks of starting therapy.
  - Patients without a diagnosis of hypophysitis who have Grade 2 hypothyroidism, Grade 2 low testosterone or Grade 2 adrenal insufficiency where clinical symptoms are controlled with appropriate hormone replacement therapy.

Rev. 11/13,  
9/14

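### Section 5.5.1.3 bars, on the ipilimumab arms, the replacement steroids that section 3.1.13 allows at entry

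*Combined protocol and SAP*

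**What the plan says.** Section 3.1.13 excludes patients who need ongoing systemic steroids or other immunosuppressants for autoimmune or immunosuppressive conditions. It treats physiologic replacement separately: "Replacement doses of steroids for patients with adrenal insufficiency are allowed". The checklist under the same criterion has an item headed "Adrenal insufficiency", so such entrants were foreseen.

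For the ipilimumab arms, section 5.5.1.3 states: "Corticosteroid replacement therapy is not allowed except for patients who develop endocrinopathies during this study that require corticosteroid replacement therapy (such as hydrocortisone". The sentence ends by requiring stable doses.

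For the interferon arms (B and E), section 5.2.2.6 opens with its reason: "Corticosteroids and other immunosuppressive medications are contraindicated during IFN Alfa-2b therapy because of immune suppressive effects". It continues: "No systemic treatment with steroids (including creams) is permitted". Its exceptions are antihistamines, inhaled steroids at doses that do not suppress immunity, and a clause under which "steroids (topical, inhaled or systemic) may be used to treat adverse events or toxicities if there is a clear clinical indication". Replacement is not mentioned.

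Section 5.6.3.1 lists chronic systemic corticosteroids among therapies prohibited during the study and makes no exception for replacement.

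**The concern.** A patient with established adrenal insufficiency on hydrocortisone can be randomized under 3.1.13. If assigned to ipilimumab, that patient meets a rule that names replacement therapy itself, prohibits it, and gives a single exception that does not fit. A site that continues the hydrocortisone departs from the text. A site that obeys the text withholds a drug the patient needs. The stake is patient safety and clean compliance records, not the efficacy comparison.

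**Working it through.** No plan figure has to be reproduced. The check is whether any provision carries the entry permission through to treatment.

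**Ipilimumab arms**

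- 3.1.13: replacement for adrenal insufficiency is permitted at entry.
- 5.5.1.3: replacement is prohibited unless the endocrine disorder arose on study. A pre-existing disorder fails that condition.
- 5.5.1.1.2 (Arms A, D) and 5.5.1.2.2 (Arms C, F): ipilimumab may not be restarted during steroid treatment of an immune-related event, "except for patients on stable doses of hormone replacement therapy for adrenal insufficiency such as hydrocortisone". This is a condition for restarting ipilimumab. It does not amend 5.5.1.3.
- The footnotes to the management algorithms in Appendices XIV to XVIII are also restart rules.
- 5.5.1.1.4 and 5.5.1.2.4: ipilimumab may be resumed in "Grade 2 adrenal insufficiency where clinical symptoms are controlled with appropriate hormone replacement therapy". This is an exception to permanent discontinuation for adverse events.
- 5.5.1.5.5 and Appendix XIII: replacement is to be started when an endocrinopathy is documented during ipilimumab work-up, which is the case 5.5.1.3 already allows.
- 5.6.1: a general commitment to optimal supportive care. It does not name replacement or displace an express prohibition.

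These provisions show that replacement was meant to be tolerated on ipilimumab. None covers a patient who is simply continuing replacement from entry.

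**Interferon arms**

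Section 5.2.2.6 gives immune suppression as its reason and bars systemic steroid treatment. Its exceptions do not include replacement taken at entry, but nothing in it names replacement as prohibited. That is a gap to clarify, not a direct contradiction.

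**Scale**

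The documents give no rate of replacement use at entry. Planned ipilimumab enrolment is 500 + 500 adults (section 9.3) plus 15 + 15 adolescents (section 9.11), or 1,030. Each 0.1% on replacement would be 0.001 × 1,030, about one patient. An assumed range of 0% to 0.5%, which has no basis in the documents, gives 0 to about 5.

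**Timing**

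Section 5.7.1 puts ipilimumab at about 60 weeks (420 days). Section 5.2.1.1 allows 7 days to the first dose, and the section 7.2 calendar allows 2 weeks around week 60, so 420 + 7 + 14 = 441 days.

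- Last adult, 15 August 2014: 441 days later is 30 October 2015.
- Last adolescent: section 9.3 says only that enrolment stays open until 2016. Assuming last entry between 1 January and 31 December 2016, planned treatment ends between 17 March 2017 and 17 March 2018. That is 700 to 335 days before the 15 February 2019 final analysis.

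Neither figure is a bound. Further dose delays and retreatment after resected recurrence (section 5.2.3) are not counted.

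**The case against.** The best defence is context. The sentence in 5.5.1.3 sits among guidance on managing immune-related events, so it can be read as governing when replacement may be started for an on-study event. The restart rules, which accept stable replacement without asking when the disorder began, fit that reading: a patient may hardly be re-dosed while taking something forbidden. Section 5.6.1 and clinical common sense point the same way. This is good evidence of intent, and it makes actual withholding unlikely. It does not change the wording, which is a prohibition on replacement with one stated exception.

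A reader might go further and infer that all six arms carry the same explicit conflict. The documents do not support that. Section 3.1.13 distinguishes immunosuppressive steroid treatment from replacement, and 5.2.2.6 follows the first idea: it pairs corticosteroids with other immunosuppressive drugs, tolerates inhaled steroids below immunosuppressive doses, and never mentions replacement. Only 5.5.1.3 names it. Likewise, the 5.6.3.1 listing need not be read as a separate conflict, given the specific provisions that accept replacement on ipilimumab.

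It can also be said that a correction is moot once treatment has ended. Late timing does reduce the urgency. It does not make the text consistent, and the exact margin cannot be established from the documents.

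**Conclusion.** The inconsistency between 3.1.13 and 5.5.1.3 is real and affects Arms A, C, D and F. It is a minor drafting error: read literally, the rule would stop medically necessary replacement in eligible patients, but the number exposed is unknown and may be zero.

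There is no effect on the efficacy analysis. The primary comparisons are by assigned treatment (sections 9.2 and 9.8.1), and these patients meet the eligibility rule, so continuing replacement does not make them ineligible for the sensitivity analysis of eligible, treated patients either.

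A reader might infer that the 3.1.13 checklist gives a count of those affected. It does not: its relevant item records adrenal insufficiency rather than replacement use, and section 3 has the checklist kept in the patient's chart. The steroid and hormone medication logs and the concomitant medication records on the section 7.2 and 7.3 calendars are the better source.

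The conclusion rests on the literal wording of 5.5.1.3. The statement that planned treatment was probably complete before the final analysis rests on the assumed last adolescent entry date and on no long delays or retreatment.

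**What to change.** In 5.5.1.3, add a second exception beside the existing one, covering patients who entered on stable physiologic replacement for adrenal insufficiency under section 3.1.13.

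As conforming clarifications, add the same entry-replacement exception to 5.2.2.6 for Arms B and E. In 5.6.3.1, qualify the entry on chronic systemic corticosteroids so that it excludes stable physiologic replacement.

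The cost is one clause in each of two sections and a short phrase in a third, made in the next amendment or a clarification memo. Eligibility, data collection and analysis do not change. It is also worth checking that replacement continued from entry was not recorded as a protocol deviation.
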